1 PROTOCOL SUMMARY

1.1 Study design

The study is a non-randomized, open label, prospective multi-center, clinical study designed to collect long-term (1 year), system-related, clinical and subject reported outcome data from subjects indicated for a de novo ablation of paroxysmal atrial fibrillation and treated with the Cryterion Cardiac Cryoablation System and components including the SmartFreeze Cryo-console, the Cryoablation Balloon Catheter, and the Circular Mapping catheter.

A protocol amendment of the original FIM protocol was initiated in May 2018 designed for the purpose of obtaining CE mark and intended to prolong the follow-up period from 30 days to 12 months and extend the number of enrolled subjects from 30 to 100.

Subjects will be followed for 12 months by each clinical center with specific scheduled visits to detect recurrent AF (Detectable AF) and adverse events (AEs).

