1.4 Endpoints

1.4.1 Primary Safety Endpoint

Safety endpoint is assessed by freedom from device or procedure related serious adverse events (referred to as Major Adverse Events, MAE) at 12 months* post-procedure.

MAEs include the following:

- Death
- Myocardial infarction
- Cardiac perforation/ pericardial tamponade
- Cerebral infarct or systemic embolism
- Major bleeding requiring transfusion of blood products
- Mitral or tricuspid valvular damage
- Phrenic nerve damage causing persistent diaphragmatic paralysis**
- Symptomatic pulmonary vein stenosis
- Atrio-esophageal fistula
- Air embolism leading to a life-threatening event such as a ventricular arrhythmia, stroke or myocardial infarction
- Any other serious or non-serious adverse device effects (SADEs or ADEs)

*For 1 Month sub-analyses this endpoint will be presented as the rate at 1 Month. Any additional endpoint events reported for subjects with longer follow-up will be noted in the report

**According to the consensus document definition: Phrenic nerve paralysis is defined as absent phrenic nerve function as assessed by a sniff test. A phrenic nerve paralysis in this study is considered to be permanent when it is documented to be present at 12 months following ablation.

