2 SUBJECT CLASSIFICATION DEFINITIONS

For the purposes of this clinical study, the following definitions regarding the status of a subject will apply:

Enrolled Subject - Any subject who has signed an informed consent form (ICF)

Consent Ineligible Subject – Any subject who has signed the informed consent but is found not to meet all the inclusion/exclusion criteria. This includes a subject who has signed an informed consent form but may be excluded based on the results of the pre-procedure TEE or intracardiac echocardiogram (ICE) evaluation of the left atrial appendage (LAA) and/or PV anatomy. In the event these subjects completed a trans-septal puncture, they will be followed through discharge for the recording of any procedure related adverse events. These subjects will not count towards the enrollment ceiling and will not be considered for the primary endpoints analysis.

Intent Subject – Any subject who has signed an informed consent form (ICF) and is deemed study eligible by meeting all the inclusion and none of the exclusion criteria but does not undergo the ablation procedure. This subject will be withdrawn from the study. Data will be collected up to the point of withdrawal, will not count towards the enrollment ceiling and will not be considered for primary endpoints analysis.

Attempt Subject - Any subject who has signed an informed consent form (ICF) and is deemed study eligible by meeting all the inclusion and none of the exclusion/criteria and undergoes the ablation procedure with any of the investigational device entered in the subjects' body but no energy is delivered to the PVs. This subject will be followed through the 30 days follow up then withdrawn from the study. Data will be collected up to the point of withdrawal, will not count towards the enrollment ceiling and will not be considered for primary endpoints analysis.

Treated Subject – Any screened subject who completes the ablation procedure to the point that any of the investigational products are introduced into the body and Cryo-energy is delivered. Enrolled subjects will be followed for all study outcome measures for the full duration of the clinical study.

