3.2 Statistical Analysis

Analysis of study endpoints will be performed on an intent-to-treat basis. All partial data that is available on subjects who drop out during the course of the study will be included.

Descriptive analysis will be used to present the study. Continuous variables will be reported as median and range, mean \pm standard deviation; categorical variables will be reported as n/N (%).

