3.3 Primary Safety Endpoint

The primary safety endpoint outcome is freedom from a composite MAE list, outlined in Section 2.4.1 above, and all other serious or non-serious adverse device effects (SADEs or ADEs).

The rate of MAEs and rate of SADEs and ADEs will each be presented separately as well as an overall combined rate of all events. Rates will be presented as the binomial rate (N events/ N subjects) with corresponding exact binomial 95% confidence interval. These rates will be compared to the safety outcome rates derived from available literature data.

Additionally, all adverse events will be summarized by type of event, severity, relationship to the device and/or procedure, and timing of event relative to the procedure date. Listings of all adverse events and separate listings of events meeting the safety endpoint will be provided.

The primary safety endpoint will be assessed in all enrolled subjects who undertake the ablation procedure to the point that the Cryoablation Balloon is inserted into the subject (Attempt and Treated subjects).

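### The 12-month safety rate is a crude proportion with no rule for incomplete follow-up, so event-free subjects who stop early count as event-free at 12 months

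*SAP*

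**What the plan says.** - **Background.** SAP Section 1.1 describes an amendment "intended to prolong the follow-up period from 30 days to 12 months and extend the number of enrolled subjects from 30 to 100", and then gives 12 months as the follow-up for subjects in general.
- **Horizon.** SAP Section 1.4.1 defines the primary safety endpoint as "freedom from device or procedure related serious adverse events (referred to as Major Adverse Events, MAE) at 12 months* post-procedure". Its footnote gives the 1-month sub-analyses a 1-month rate instead.
- **Estimator.** Section 3.3: "Rates will be presented as the binomial rate (N events/ N subjects) with corresponding exact binomial 95% confidence interval". The result is then set against rates from the literature.
- **Denominator.** Section 3.3 takes in subjects who reach the "point that the Cryoablation Balloon is inserted into the subject (Attempt and Treated subjects").
- **Attempt subjects.** Section 2: "This subject will be followed through the 30 days follow up then withdrawn from the study". The sentence after it reads "Data will be collected up to the point of withdrawal, will not count towards the enrollment ceiling and will not be considered for primary endpoints".
- **Dropouts.** Section 3.2: "All partial data that is available on subjects who drop out during the course of the study will be included". Section 3.1.1 runs the overall analysis once every subject has finished or been withdrawn.
- **Contrast.** Section 3.5 makes subjects who leave before the 12-month visit without an event ineligible for the 12-month effectiveness analysis. Section 3.3 has no counterpart.
- **Phrenic nerve component.** Section 1.4.1: paralysis "is considered to be permanent when it is documented to be present at 12 months" after ablation.

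**The concern.** A proportion of the form events over subjects is a 12-month risk only if everyone in the denominator was either observed for 12 months or had the event. Section 3.3 does not require this, and for Attempt subjects the plan itself ends observation at 30 days. An event-free subject who stops early stays in the denominator and can add nothing further to the numerator, which is the same as recording 12 event-free months.

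The study has one arm, and the only use stated for the rate is comparison with published rates. A downward error therefore favours the device. The exact binomial interval also treats every subject as fully observed.

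The SAP shows elsewhere that it sees the issue: Section 3.5 has a rule for early withdrawal, and the footnote in Section 1.4.1 matches the horizon to the follow-up in the sub-analyses. The primary safety analysis has neither.

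**Working it through.** **No plan figure to reproduce.** The SAP gives no expected event rate, and its sample size section is redacted. Every rate and count below is an assumption chosen to show scale.

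**Step 1: formula.** Let f be the share of the safety denominator last observed at day 30 without later follow-up, e the event probability by day 30, and l the probability of a first event from day 31 to month 12. Suppose first that l is the same in those who stop.

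- True 12-month risk = e + l
- Expected crude rate = e + (1 − f) × l
- Shortfall = f × l

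The shortfall cannot be negative. It is zero if nobody stops early or if no event occurs after day 30.

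**Step 2: size, in percentage points.**

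| Share stopped at day 30 (f) | l = 1% | l = 2% | l = 5% |
|---|---|---|---|
| 2% | 0.02 | 0.04 | 0.10 |
| 5% | 0.05 | 0.10 | 0.25 |
| 30% (not documented) | 0.3 | 0.6 | 1.5 |

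With e = 5%, the last row is a relative understatement of 0.3/6 = 5%, 0.6/7 = 8.6% and 1.5/10 = 15%.

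**Step 3: which estimator.** Take 100 subjects, with 5 events by day 30 and 3 later.

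*Five event-free subjects stop at day 30.* At risk afterwards: 100 − 5 − 5 = 90.
- Crude: 8/100 = 8.0% (exact 95% CI 3.5–15.2%)
- Kaplan-Meier: 1 − 0.95 × (1 − 3/90) = 8.2%
- Section 3.5 rule (event-free leavers removed): 8/95 = 8.4%

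*Thirty stop at day 30, two of them having had an early event.* At risk afterwards: 70 − 3 = 67.
- Crude: 8/100 = 8.0%
- Kaplan-Meier: 1 − 0.95 × (1 − 3/67) = 9.3%
- Section 3.5 rule: 8/72 = 11.1% (exact 95% CI 4.9–20.7%)

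The crude rate is too low. Carrying the Section 3.5 rule over to safety errs the other way, because it keeps the early events of those who left and discards their event-free companions.

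**Step 4: the denominator.** Section 3.3 names Attempt subjects as part of the safety population. Section 2 says they are not considered for the primary endpoints, of which safety is one. Both cannot be followed. Under Section 3.3, planned 30-day follow-up enters a 12-month rate. Under Section 2 that part of the bias goes, but other early dropouts remain through Section 3.2.

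**The case against.** The strongest objection concerns size. Attempt subjects and dropouts may be few, most complications of an ablation may be peri-procedural, and a shortfall of 0.02–0.25 points is negligible beside an exact interval of 3.5–15.2% for 8/100. The analysis is descriptive, and Section 3.3 already asks for events to be summarized by timing. This stands as a limit on importance. It does not supply the missing rule, and a summary of event times does not turn the crude rate into a 12-month risk.

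Three stronger readings are tempting and are not supported.

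- *A reader might infer from Section 1.1 that the first 30 subjects were observed for only 30 days.* The sentence is amendment history. The text after it says subjects are followed for 12 months, with no exception, and Section 2 has Treated subjects followed for the whole study. The SAP does not say how subjects already enrolled were handled, so the 30% row is an undocumented worst case.
- *A reader might take the understatement as certain.* It is conditional on events occurring after subjects stop. Attempt subjects received no energy to the pulmonary veins, so their later risk may be below that of Treated subjects and the shortfall from them smaller than f × l.
- *A reader might conclude that phrenic nerve injury is lost altogether in subjects seen for 30 days.* Permanence cannot be established in them, which affects the separate MAE rate. A device-related palsy seen by day 30 would still count as an adverse device effect in the combined rate.

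**Conclusion.** The point holds in limited form. Followed as written, Section 3.3 scores subjects who stop early without an event as event-free at 12 months. The resulting error can only be downward. Its likely size is small: 0.02–0.25 percentage points if 2–5% stop at day 30 and later risk is 1–5%, all of which are assumptions. The 0.3–1.5 point range needs 30% stopped at day 30, for which the SAP gives no evidence.

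The contradiction between Sections 2 and 3.3 over Attempt subjects needs no assumption. It should be settled first, because it decides whether any subject enters a 12-month rate with follow-up planned to end at 30 days.

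**What to change.** 1. Reconcile Section 2 with Section 3.3 on whether Attempt subjects belong to the primary safety denominator.
2. In Section 3.3, report 12-month freedom from the safety endpoint by Kaplan-Meier with a log-log 95% CI, censoring at last contact, beside the planned binomial rate. If Attempt subjects stay in, note that censoring them at 30 days gives them the later risk of those still followed.
3. Report the number with complete 12-month follow-up and the number, if any, followed for only 30 days, including any from the original protocol.
4. Give a separate 1-month rate on all subjects in the safety denominator.
5. Do not use a rate restricted to completers and subjects with events as the estimate, since it overstates risk.

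The cost is SAP wording, one more table and a slightly wider interval. No additional data collection is required.

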1.2 Study devices

The Cryterion Cardiac Cryoablation System is designed to thermally ablate cardiac tissue in the management of atrial fibrillation. The components and accessories for the system are listed below:

- Cryoablation Balloon Catheter
- Cryo-Console
- Circular Mapping Catheter
- Steerable Sheath, 12 F
- Diaphragm Movement Sensor
- Esophageal Temperature Sensor Cable
- Inter Connection Box
- Cryo-Console Foot Switch

- Cryo-Cable
- Cryo-Catheter Extension Cable
- EP Electrical Cable

1.3 Follow-up

Visits include Screening & Baseline, Index Procedure, Discharge, 1 Month, 3 Months, 6 Months and 12 Months and additional follow-up visits (including potential repeat procedures).

1.4 Endpoints

1.4.1 Primary Safety Endpoint

Safety endpoint is assessed by freedom from device or procedure related serious adverse events (referred to as Major Adverse Events, MAE) at 12 months* post-procedure.

MAEs include the following:

- Death
- Myocardial infarction
- Cardiac perforation/ pericardial tamponade
- Cerebral infarct or systemic embolism
- Major bleeding requiring transfusion of blood products
- Mitral or tricuspid valvular damage
- Phrenic nerve damage causing persistent diaphragmatic paralysis**
- Symptomatic pulmonary vein stenosis
- Atrio-esophageal fistula
- Air embolism leading to a life-threatening event such as a ventricular arrhythmia, stroke or myocardial infarction
- Any other serious or non-serious adverse device effects (SADEs or ADEs)

*For 1 Month sub-analyses this endpoint will be presented as the rate at 1 Month. Any additional endpoint events reported for subjects with longer follow-up will be noted in the report

**According to the consensus document definition: Phrenic nerve paralysis is defined as absent phrenic nerve function as assessed by a sniff test. A phrenic nerve paralysis in this study is considered to be permanent when it is documented to be present at 12 months following ablation.

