1.4.4 Secondary Endpoints

Secondary Endpoint Measurements will include:

- All Procedure and device related adverse events*
- Documentation of all targeted PVs that demonstrate isolation immediately post ablation and then show reconnection during entrance/exit block testing
- Recording of time to demonstration of PVI using the Circular Mapping catheter following the initiation of a freeze cycle
- Operator's assessment of handling characteristics with a System Performance Questionnaire**

* be accessed directly from the clinical database (eCRFs hosted on IBM Clinical platform)

** The System Performance Questionnaire is included in the study clinical database and includes questions to the operator to assess quality characteristics of the products, alone and compared to commercially available cryoballoon ablation technologies and circular mapping catheters. The system performance questionnaire will be used with all new clinical users for the first five (5) cases performed with the Cryterion System. After the first 5 cases, users can use the questionnaire to provide specific product feedback related to user experience(s) on an as needed basis (for example: the ability of the cryoablation system to deal with tortuous anatomy of the LA/PVs). In case the investigator reports quality issues in the questionnaire, he should consider if needed, to enter a device deficiency

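### The primary safety endpoint is defined as serious events related to device or procedure, but its catch-all and the analysis rule add only device effects, so the SAP supports two different primary safety rates

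*SAP*

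**What the plan says.** Section 1.4.1 of the SAP opens with the definition: "Safety endpoint is assessed by freedom from device or procedure related serious adverse events (referred to as Major Adverse Events, MAE"). It introduces the components with "MAEs include the following", names ten events from death to air embolism, and closes with one catch-all: "Any other serious or non-serious adverse device effects (SADEs or ADEs").

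Section 3.3, which governs the analysis, states the outcome as "freedom from a composite MAE list, outlined in Section 2.4.1 above, and all other serious or non-serious adverse device effects (SADEs or ADEs"). (The cross-reference evidently means section 1.4.1.) On reporting it says: "The rate of MAEs and rate of SADEs and ADEs will each be presented separately as well as an overall combined rate of all events". The estimator is given as: "Rates will be presented as the binomial rate (N events/ N subjects) with corresponding exact binomial 95% confidence interval". These rates are then to be set against safety rates from the literature.

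Procedure-related events appear by name in two other places. Section 1.4.4 has the secondary endpoint "All Procedure and device related adverse events". The general adverse event summary in section 3.3 breaks events down by, among other things, relatedness to device and to procedure. The SAP does not define ADE or SADE.

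**The concern.** The defining sentence has two limbs, device and procedure. The catch-all and the rule in section 3.3 carry only the device limb. A serious event that is procedure-related only and off the named list meets the definition but matches no listed item. Examples are an anaesthetic complication that prolongs the hospital stay, or a transient ischaemic attack without infarct, when judged unrelated to the device.

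The catch-all also admits non-serious device effects. On the narrower reading, a minor device effect would make a subject an endpoint failure while a serious procedural complication off the list would not.

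What is at stake is the primary safety rate itself: the figure that carries the exact interval and goes into the literature comparison. If its scope is not fixed, the result can depend on whether an event is attributed to the device or to the procedure. The study is open label and uncontrolled, so that choice should be settled in the plan.

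**Working it through.** The SAP states no safety rate or performance goal that bears on this point, and its sample size section is redacted. There is no figure to reproduce. The check is a comparison of wording, followed by a sensitivity calculation.

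**Scope of each statement in the SAP**

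| Place | Named events | Other serious device effects | Non-serious device effects | Other serious procedure-only events |
|---|---|---|---|---|
| 1.4.1, defining sentence | if related and serious | yes | no | yes |
| 1.4.1, list taken literally | yes (ten) | yes | yes | no item |
| 3.3, outcome and rates | yes | yes | yes | no item |
| 1.4.4, secondary endpoint | if related | yes | yes | yes |

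The last column is the point: the defining sentence and the analysis rule disagree.

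**Closed or open list?**

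1. The word include in section 1.4.1 permits an open list. The defining sentence then brings the event in as an MAE, and it counts in the MAE rate.
2. Section 3.3 speaks of a composite list and adds device effects to it as a separate component. That suggests the MAE list there means the ten named items, so the event has no place in any of the three rates. This is not conclusive, because section 3.3 repeats an item that section 1.4.1 already lists.
3. Device effects are unlikely to include procedure-only events by implication, since sections 1.4.4 and 3.3 treat the two relationships as distinct.

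Both readings can be defended from the text, and they give different counts.

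**Sensitivity**

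Inputs: 100 subjects planned (section 1.1); sub-analyses on the first 50 and the first 30 (section 3.1.1). Assumption: the safety denominator equals these numbers. It may differ slightly, since section 3.3 uses Attempt and Treated subjects.

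Each affected subject with no other counted event shifts the rate by 1/N: 1/100 = 1.0, 1/50 = 2.0 and 1/30 = 3.3 percentage points.

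Exact (Clopper-Pearson) 95% limits for x of N: lower = Beta quantile 0.025 with parameters (x, N−x+1); upper = Beta quantile 0.975 with parameters (x+1, N−x). Assume, for illustration only, that 3 subjects count on either reading and that 0, 1 or 2 more have only an off-list, procedure-only serious event:

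| N | 0 more (readings agree) | 1 more | 2 more |
|---|---|---|---|
| 100 | 3.0% (0.6–8.5) | 4.0% (1.1–9.9) | 5.0% (1.6–11.3) |
| 50 | 6.0% (1.3–16.5) | 8.0% (2.2–19.2) | 10.0% (3.3–21.8) |
| 30 | 10.0% (2.1–26.5) | 13.3% (3.8–30.7) | 16.7% (5.6–34.7) |

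The first column is the closed-list result throughout. The other columns are the open-list result if such events occur. The counts are not taken from the SAP, which supports no particular number.

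**The case against.** A reader might infer that the SAP excludes these events outright and therefore understates the safety rate. The text does not go that far, for these reasons.

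- **The list may be open.** Section 3.3 sends the reader back to the section that holds the two-limbed definition, and the list there is introduced by a word that need not be exhaustive. This stands: exclusion is one reading. It does not remove the problem, because a plan should not leave the primary count to interpretation.
- **The device-effect terms are undefined here.** They may be defined in the protocol, which was not available for this point. Section 1.2 lists the 12 F steerable sheath among the system's components and accessories, so some access-site or transseptal injuries might qualify as device effects. This stands, and for that reason such injuries are not used as examples above. A broad protocol definition would narrow the gap.
- **The events are reported anyway.** This also stands. They fall under the secondary endpoint in section 1.4.4, for which section 3.6 plans rates and intervals if binary, and in the adverse event summaries and listings. Safety reporting as a whole is not deficient; the issue is confined to the primary rate.
- **The direction is unknown.** The event definitions behind the literature rates are not given. If those sources use named complication lists, adding procedure-only events would make the comparison less like-for-like. Counting non-serious device effects already pushes the combined rate up. A claim of understatement against the literature is not supported.
- **A named list with a device catch-all is a legitimate composite.** It is, but the opening sentence does not describe that composite.

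Nor does the SAP say who assigns relatedness or whether events are adjudicated, so nothing here shows that the investigator alone decides.

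**Conclusion.** The inconsistency is real and lies in the definition of the primary safety endpoint. Section 1.4.1 promises freedom from serious events of either relationship, whereas the catch-all and section 3.3 extend the named list only to device effects. The SAP therefore allows two primary safety rates. They differ only if subjects occur whose sole qualifying event is serious, procedure-only and off the list.

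Per such subject the difference is 1.0, 2.0 or 3.3 percentage points for 100, 50 or 30 subjects, so the smaller regulatory cohorts are the most sensitive. How many such subjects there would be cannot be judged from the SAP, nor can the net effect on the literature comparison. The conclusion assumes that the protocol does not define adverse device effects so widely that they include procedure-only events. The analysis is descriptive and no visible threshold would be crossed, so this calls for a correction of wording and does not undermine the design.

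**What to change.** Reconcile sections 1.4.1 and 3.3 to the stated definition:

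- In section 1.4.1, add an item for any other procedure-related serious adverse event, and state that the list is then exhaustive.
- In section 3.3, count these events in the overall combined rate.
- Keep the rate for the ten named events and the SADE/ADE rate as separate lines, so that a comparison with literature using named complication lists remains possible.
- Correct the cross-reference so that it points to section 1.4.1.

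Check the wording against the protocol's endpoint and its ADE and SADE definitions. If the protocol shows that a closed list was intended, narrow the defining sentence and state the omission openly. Either way, settle the rule without reference to the event counts and apply it to the 30- and 50-subject sub-analyses as well as the full cohort.

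The cost is small. Section 3.3 already plans to summarise events by relatedness to device and procedure, so no new data item is evident. The combined rate may come out slightly less favourable, and the protocol check may show that the protocol text needs to be aligned too.
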